8.15 Photography

At a limited number of pre-selected trial sites, the target lesion/location selected for the Investigator's Assessment of the Severity of the Target Lesion/Location (Redness, Thickness, Scaliness) may be photographed.

Photographs will only be taken for subjects where additional photograph-specific informed consent has been obtained. Participating in the imaging assessments is entirely voluntary, and subjects who do not wish to have images collected will still be invited to participate in the trial without being part of the trial sub-population from which images are collected.

The designated sites will use their own equipment to take colour photographs and these imaging assessments will be performed according to local regulations.

Photographs will only be taken of the psoriasis target lesion/location affecting the trunk and limbs and the images will only be used as supportive data to the clinical assessments (i.e. there will be no adjudication of images or statistical analysis).

Subjects' name or other identifying information will not be used in the trial photographs or in any later use of the photographs.

Images will be collected at each trial visit. The recommendation of images to be collected includes:

- Anatomical Image, used to confirm the location of the target lesion/location
- Macro Image

The location of the target lesion/location will be recorded by means of a visual representation in the source records and printed copies of the photographs must be included as part of the individual subject source documentation.

LEO may at its discretion use the photographs in publications, posters and similar types of information material or media targeting patients and health care professionals. The photographs can also be part of training material used for training and educational purposes.

8.16 Investigator Assessments

All dermatologic assessments of the treatment area must be performed by a dermatologist, certified physician's assistant, advanced registered nurse practitioner or general practitioner experienced in treating psoriasis vulgaris. The same person should attempt to perform all dermatologic examinations of each individual subject.

8.16.1 Definition of the body areas to be assessed (treatment areas)

The body areas which are to be assessed are the trunk and limbs.

The trunk and limbs includes the arms* and trunk** and the legs***.

*) arms include the back of the hands

**) trunk includes the neck

***) legs include the buttocks and the top of the feet

The face, scalp, genitals and skin folds (i.e. the axillae, the inguinal folds, the inter-gluteal folds and the infra-mammary folds) are not to be treated with the IPs or assessed as part of the efficacy analysis. Also palms and soles are excluded.

The (sub)investigator must make the assessments described below. Ideally, all assessments for a subject should be made by the same (sub)investigator.

8.16.2 Physician's Global Assessment of Disease Severity (PGA)

From screening, and at all monthly visits during the maintenance phase, as well as all unscheduled visits, the (sub)investigator will make a global assessment of the disease severity of psoriasis of the trunk and limbs using the 5-point scale specified in [Table 10](#). This assessment will represent the average lesion severity on the trunk and limbs. The assessment will be based on the condition of the disease at the time of evaluation, and not in relation to the condition at a previous visit.

Table 10: Disease Severity Grading – Physician's Assessment

Clear (=0)	Plaque thickening = no elevation or thickening over normal skin Scaling = no evidence of scaling Erythema = none (no residual red colouration but post-inflammatory hyperpigmentation may be present)
Almost clear (=1)	Plaque thickening = none or possible thickening but difficult to ascertain whether there is a slight elevation above normal skin level Scaling = none or residual surface dryness and scaling Erythema = light pink colouration
Mild (=2)	Plaque thickening = slight but definite elevation Scaling = fine scales partially or mostly covering lesions Erythema = light red colouration
Moderate (=3)	Plaque thickening = moderate elevation with rounded or sloped edges Scaling = most lesions at least partially covered Erythema = definite red colouration
Severe (=4)	Plaque thickening = marked elevation typically with hard or sharp edges Scaling = non-tenacious scale predominates, covering most or all of the lesions Erythema = very bright red colouration

Note: At Day 0 (Visit 1) disease severity must be graded as at least 'Mild' in order to meet inclusion criterion No. 6.

8.16.3 Physician's Assessment of the Extent and Severity of Clinical Signs (Redness, Thickness, Scaliness) (m-PASI)

From baseline (Visit 1), and at all monthly visits during the maintenance phase, as well as all unscheduled visits, the (sub)investigator will make assessments of the extent and severity of clinical signs of the subject's psoriasis. Assessment is not made for the head (i.e. the face and scalp). Hence, this PASI assessment is modified to exclude the head.

The **extent** of psoriatic involvement will be recorded for each of the three areas (arms, trunk and legs) using the following scale:

0 = no involvement

1 = < 10%

2 = 10 - 29%

3 = 30 - 49%

4 = 50 - 69%

5 = 70 - 89%

6 = 90 - 100%

This assessment of extent is the percentage of that body area that is affected, and **not** the percentage global BSA affected (see section 8.16.4). For example, if one arm was totally affected, and the other arm was totally unaffected, the extent assessment for the arms would be 50% (half of the arms affected).

The **severity** of the psoriatic lesions in each of the three areas will be recorded for each of the clinical signs of redness, thickness and scaliness. For each clinical sign, a single score, reflecting the average severity of all psoriatic lesions on given body region, will be determined according to the following scale:

Redness

0	=	none (no erythema)
1	=	mild (faint erythema, pink to very light red)
2	=	moderate (definite light red erythema)
3	=	severe (dark red erythema)
4	=	very severe (very dark red erythema)

Thickness

0	=	none (no plaque elevation)
1	=	mild (slight, barely perceptible elevation)
2	=	moderate (definite elevation but not thick)
3	=	severe (definite elevation, thick plaque with sharp edge)
4	=	very severe (very thick plaque with sharp edge)

Scaliness

0	=	none (no scaling)
1	=	mild (sparse, fine scale, lesions only partially covered)
2	=	moderate (coarser scales, most of lesions covered)
3	=	severe (entire lesion covered with coarse scales)
4	=	very severe (very thick coarse scales, possibly fissured)

PASI:

The following formula will be used to calculate the m-PASI:

Arms 0.2 (R + T + S)E = X

Trunk 0.3 (R + T + S)E = Y

Legs 0.4 (R + T + S)E = Z

Where: R = score for redness; T = score for thickness; S = score for scaliness; E = score for extent.

The sum of X + Y + Z gives the m-PASI which can range from 0 to 64.8.

8.16.4 Investigator's Assessment of the Body Surface Area (BSA) Involvement of Psoriasis Vulgaris on Trunk and Limbs

From baseline (Visit 1), and at all monthly visits during the maintenance phase, as well as all unscheduled visits, the (sub)investigator will assess the extent of the subject's psoriatic involvement on the trunk and limbs. The total psoriatic involvement on the trunk and limbs (excluding skin folds and genitals) will be recorded as a percentage of the total BSA, estimating that the surface of the subject's full, flat palm (including the five digits) correlates

to approximately 1% of the total BSA. The purpose of this is to obtain an estimate of the area on the trunk and limbs to be treated with trial medication.

8.16.5 Investigator's Assessment of the Severity of the Target Lesion/Target Location (Redness, Thickness, Scaliness)

At Visit 1 (baseline), the (sub)investigator will select a target lesion/target location. The target lesion/location should be at least 3 cm at its longest axis located on the body (i.e., not on the scalp, face or intertrigous areas). The location will be recorded in the eCRF as trunk, limb excluding elbow/knee, elbow or knee, and in more detail in the subject medical records to allow identification of the target lesion/location at subsequent visits.

From baseline (Visit 1), and at all monthly visits during the maintenance phase, as well as all unscheduled visits, the (sub)investigator will assess the severity of the target lesion/location for each clinical sign (redness, thickness, scaliness) according to the same scale as for the Investigator's Assessment of the Severity of Clinical Signs (redness, thickness, scaliness). At Visit 1, the scoring of the target lesion/location should be at least 1 for each of redness, thickness and scaliness, and at least 4 in total (see section [8.16.3](#) for scores).

8.17 Dispensing of IP

Refer to section [10.7.1](#)

8.18 Return of IP and Compliance

Refer to sections [10.7.1](#) and [10.7.3](#)

8.19 End of Trial Form

The End of Trial Form must be completed for all subjects who have signed informed consent. This includes e.g. date of last dose, last attended scheduled visit number, primary reason for withdrawal, etc.

9 Adverse Events

- Adverse events and serious adverse events are defined in [Appendix 4: Definitions of Adverse Events and Serious Adverse Events](#)
- Classification of AEs in terms of severity, causality and outcome are defined in [Appendix 5: Classification of Adverse Events](#).

9.1 Collection of Adverse Events

AEs, including events of rebound, must be collected from time of first trial-related activity after the subject has signed the informed consent form until the FU3 visit. Refer to section [11.3.6.2](#) for a definition of rebound.

Abnormal findings observed at the screening visit should be recorded as diagnoses in the Concomitant Medication page if medication is currently being taken for the condition. If not, it will be documented as medical history in the eCRF.

AEs must be assessed by medically qualified personnel.

At all visits during the treatment phases, the subject will be asked a non-leading question by the (sub)investigator about AEs, for example: "How have you felt since I saw you last?" No specific symptoms should be asked for. It is important that the (sub)investigator also observes the subject for any changes not reported by the subject and records these changes.

9.1.1 Application site reactions: Assessment of local safety and tolerability

Application site reactions (perilesional erythema, oedema, dryness, erosion and burning and pain) which match the criteria in the Local Safety and Tolerability Scale (see Section [8.11](#)) are not to be reported as AEs in the eCRF even if they require treatment. Application site reactions other than those identified in the Local Safety and Tolerability scale must be recorded appropriately as AEs. Any application site reaction classified as SAEs must be added to the AE form in the eCRF and in addition reported to LEO on the SAE Form (according to "Investigator Reporting Responsibilities", Section [9.4.1](#)). Any treatment for an application site reaction must be recorded on the concomitant medication page of the eCRF.

9.2 Reporting of Adverse Events in the eCRF

AEs reported by the subject or observed by the (sub)investigator must be recorded on the AE form of the eCRF and should be described in the following manner:

The *AE term* will be in precise English medical terminology (i.e. not necessarily the exact words used by the subject). Whenever possible, a specific diagnosis should be stated (e.g. allergic contact dermatitis).

For cutaneous AEs the *location* must be part of the AE description and may be described as e.g. the face, scalp, back, chest, arm, leg, trunk or limb.

Additionally, the location should be described using the following terminology:

- Lesional/perilesional (≤ 2 cm from the area(s) treated with IPs) or
- distant (>2 cm from the area(s) treated)

The *duration* of the AE must be reported as the start date and stop date of the event. In addition, it must be recorded whether the AE started prior to start of trial medication.

AEs must be classified in terms of severity, causality and outcome according to the definitions in [Appendix 5: Classification of Adverse Events](#).

9.2.1 Additional requirements for reporting of adverse events of concern associated with long-term topical corticosteroid use

If the (sub)investigator considers an AE to be one of concern associated with long-term topical corticosteroid use, this should be indicated in the AE section of the eCRF, and will require a detailed narrative of the AE to be entered, including a description of the clinical course, the area(s) affected if a cutaneous event (body location and approximate size), and predisposing concomitant conditions, medications, or history.

If LEO suspects that an AE may be one of concern associated with long-term topical corticosteroid use, LEO may ask the (sub)investigator to provide additional information.

The purpose of collecting these additional data is to provide as much information as possible on suspected events in order to aid the adjudication of events by the Adjudication Panel.

9.2.2 Actions Taken as a Consequence of an AE

Action taken with trial treatment: Any action taken with trial medication as a consequence of the AE must be recorded (dose not changed, drug interrupted, drug withdrawn, not applicable, unknown).

Note regarding AEs of concern associated with long-term corticosteroid use: A (sub)investigator may consider an AE to be one of concern associated with long-term topical corticosteroid use and may wish to manage such an event by temporarily or permanently stopping trial medication usage. Such a change in trial medication usage may apply to just the area(s) affected by the event, or its total use. Such a change in trial medication usage must be documented in the eCRF.

Other action taken: Any other action taken as a result of the AE must be recorded (none, concomitant medication, concurrent procedure).

Withdrawn due to AE: It must be recorded whether the AE leads to withdrawal from the trial.

9.3 Other Events to be Reported

9.3.1 Pregnancy

Any pregnancy occurring during the clinical trial must be reported to LEO within 24 hours of first knowledge using the (paper) Pregnancy Follow Up Form (Part I). All such pregnancies must be followed up until delivery or termination and final outcome must be reported on the (paper) Pregnancy Follow Up Form (Part II) within 24 hours of first knowledge.

The completed Pregnancy Follow Up Forms must be faxed or scanned and e-mailed to Global Pharmacovigilance (GPV), LEO (see section [9.4.1](#) for contact details).

Please also confer with section [7.9](#), Discontinuation.

9.3.2 Overdose

Overdose refers to the administration of a quantity of a medicinal product given per administration or per day which is above the protocol defined dosage.

In this clinical trial, the use of more than one 60g can in 4 days is considered an overdose.

The term overdose must be documented on the AE form in the eCRF. In addition, AEs originating from overdose must be documented on a separate line.

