Data from several small trials with intermittent use of topical corticosteroids indicate that twice-weekly application on weekends is an effective and safe regimen. The twice-weekly regimen used in this trial with 3 or 4 days between applications has been selected based on a

discussion with a panel of dermatologists. This regimen is justified by published data and in-house studies as outlined below. There is broad consensus in the literature that the stratum corneum can act as a reservoir for topically applied drugs and that this can reduce the frequency of applications (17). The effect of clobetasol propionate applied topically on rabbit skin was studied by Abidi et al. (18) who concluded that a single dose maintained full anti-inflammatory effect for 4 days. Proprietary data on calcipotriol/BDP combination products suggest that the half-life in the skin is approximately 3 days (19, 20). These data support the effectiveness of a twice-weekly regimen with 3 or 4 days between applications.

The maximum allowance of maintenance IP during maintenance phase is set at 3 cans (3 x 60 g) for 4 weeks. This ensures that subjects will have sufficient maintenance IP to use up to 15 g/day (maximum daily dose according to the product labeling) twice weekly during each 4-week period. Note that due to the visit window of +/- 4 days, subjects may need up to 9 applications during a 4-week period. This amount is considered adequate as 15 g is sufficient to cover more than 30% of body surface area (BSA), and it is supported by previous experience from LEO 90100 clinical trials where subjects with extensive psoriasis (15-30% of BSA) used on average 9 g per day, and subjects in short-term efficacy and safety trials used on average less than 5 g.

Subjects

In order to qualify for the trial, subjects must meet the inclusion/exclusion criteria, which are designed to select a population that is representative for the target population and are consistent with the criteria used in the short-term pivotal trials in psoriasis vulgaris; i.e., subjects of all disease severities amenable to topical therapy, with psoriasis lesions on the trunk and/or limbs involving between 2-30% of BSA. The eligibility criteria are selected to prevent any confounding issues with diagnosis and minimize any possible effect of concurrent diseases or concomitant medications on clinical assessment.

Assessments and endpoints

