10.2 Administration of Investigational Products

The administration of IP is described in [Table 13](#).

Table 13: Administration of Investigational Products

Route of administration	Topical
Dosing range	Not applicable
Dosing frequency	
Initial open-label treatment phase: LEO 90100 once daily for 4 weeks
 
Maintenance phase: randomised maintenance IP twice weekly 3 or 4 days apart.
 
In case of relapse: Rescue IP once daily for 4 weeks on active lesions.

Weekly maximum	
Initial open label phase: 100 g per week
 
Treatment of relapse: 100 g per week for daily treatment
 
Maintenance phase: 30 g per week (15 g per day)

Time of day for dosing	No specific requirements
Relation of time of dosing of rescue IP and maintenance IP during relapse (on days requiring application of both IPs)	Maintenance IP before rescue IP
Relation of time of dosing to clinical assessments	Preferably no dosing within 2 hours prior to the site visit

At Visit 1, the subject will be given a treatment instruction sheet describing the scenarios to be considered depending on the different treatment phases and they will receive verbal instruction about how to apply the trial medication.

- During the initial open-label treatment phase, subjects will be asked to apply LEO 90100 once daily on the affected areas on trunk and limbs for 4 weeks. At Visit 2 (after 4 weeks), subjects will have to return all containers with trial medication and, if they have achieved treatment success (PGA score of 'clear' or 'almost clear' with at least a 2-grade improvement from baseline), they will be dispensed new (blinded) medication according to the randomisation scheme.

- During the maintenance phase, subjects will apply maintenance IP twice weekly on trunk and limbs to areas where lesions have cleared or almost cleared after treatment was initiated at baseline. Any new psoriatic lesions that have been cleared by rescue treatment during relapse phase should be treated with maintenance IP as well. The treatment should be applied 3 or 4 days apart. The choice of the application days (two days) should be left to subjects' preference (e.g., Thursday and Sunday); these days will be fixed at Visit 2, recorded in the eCRF and subjects will be asked to keep the selected days throughout the trial. To improve medication adherence, electronic reminders will be sent to the subject every week on the selected application days.

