- Following confirmation of a relapse during the maintenance phase, subjects will be asked to apply rescue IP once daily on the active psoriatic lesions on trunk and limbs for 4 weeks, while continuing twice-weekly maintenance treatment on non-active lesions. Rescue IP will be dispensed at the visit when relapse is confirmed. The rescue IP will be stopped after 4 weeks at a scheduled visit or at a relapse follow-up visit, as applicable.

The first application of the IP should be made under supervision and instruction of a member of the trial staff or at home the same day the subject attended Visit 1. The IPs will be dispensed by a designated person. As described above, there will be different types of instructions for initial open-label, maintenance and relapse treatment phases. Subjects will always be reminded which instruction(s) to follow during the next 4-week period.

When an application is to be administered on the same day as a trial visit, it should not be administered within 2 hours of the site visit.

Missed application during the maintenance phase:

LEO 90100 should be applied twice weekly 3 or 4 days apart on specific days. If an application is missed, the medication should be applied as soon as subject remembers. The next application should be made at the next scheduled dosing date.

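### The single overdose threshold in protocol section 9.3.2 fits once-daily treatment but does not match the Table 13 maxima for combined use in relapse or for maintenance alone

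*Protocol*

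**What the plan says.** Protocol section 9.3.2 opens with a general definition of overdose: a quantity "given per administration or per day which is above the protocol defined dosage". It then gives a rule specific to this trial: "the use of more than one 60g can in 4 days is considered an overdose". The rule names neither a phase nor a product. An overdose has to be entered on the AE form.

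Table 13 in protocol section 10.2 sets weekly maxima line by line: "Initial open label phase: 100 g per week"; "Treatment of relapse: 100 g per week for daily treatment"; and "Maintenance phase: 30 g per week (15 g per day". The two once-daily lines carry no daily figure. Section 3.3.3 explains the maintenance supply as enough for a subject to "use up to 15 g/day (maximum daily dose according to the product labeling" on two days a week.

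In relapse, section 10.2 has subjects apply rescue product once daily "while continuing twice-weekly maintenance treatment on non-active lesions". Table 13 also gives an order of application "on days requiring application of both IPs". Section 10.4 supplies 7 cans of rescue product per relapse and 3 cans of maintenance product every 4 weeks. No maximum is stated for the two products together.

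**The concern.** An overdose definition anchored to the protocol dosage should classify use the same way as the dosage table does. Here one figure serves three situations with different limits. In relapse, a subject who stays within both Table 13 lines might still be recorded as an overdose. In remission, a subject who uses maintenance product well above its weekly line might not be.

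Overdose becomes an AE entry, and SAP section 5.5.3 tabulates AEs by arm and also by randomised treatment split by rescue use. A rule that leans one way in relapse and the other in remission could make those entries hard to compare across that split. It could also affect the comparison between arms if relapse rates differ. Long-term corticosteroid safety is a main objective of the trial, so excess use should be labelled consistently.

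**Working it through.** **Inputs.** Threshold: 60 g in 4 days (section 9.3.2). Maxima: 100 g/week open-label, 100 g/week rescue, 30 g/week and 15 g/day maintenance (Table 13). Maintenance applications are 3 or 4 days apart (section 10.2), so a 4-day window holds one or two. Supply: 7 rescue and 3 maintenance cans of 60 g per 4 weeks (section 10.4). Average use: 9 g/day with 15-30% of BSA affected (section 3.3.3).

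**1. Where the threshold comes from.** 15 g/day × 4 days = 60 g. Also, 7 cans × 60 g / 28 days × 4 days = 60 g. Both reproduce the stated figure. As a weekly amount it is 60 / 4 × 7 = 105 g.

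**2. Once-daily product alone.** 100 / 7 × 4 = 57.1 g per 4 days, below 60 g. Even use at the maximum does not trigger the rule. Uneven use can: four days at 16 g and three at 12 g total 100 g in the week, but 4 × 16 = 64 g falls in 4 days.

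**3. Relapse, both products at their maxima and counted together.**

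| Maintenance applications in window | Rescue | Maintenance | Total in 4 days |
|---|---|---|---|
| One | 57.1 g | 15 g | 72.1 g |
| Two | 57.1 g | 30 g | 87.1 g |

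The average is (100 + 30) / 7 × 4 = 74.3 g. With maintenance at 15 g per application, the pooled total reaches 60 g when rescue use is (60 − 15) / 4 × 7 = 78.75 g/week with one application in the window, or (60 − 30) / 4 × 7 = 52.5 g/week with two. The cans supplied would allow (7 + 3) × 60 / 28 × 4 = 85.7 g per 4 days.

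**4. Relapse at the reported average.** Assume 9 g per application of either product. Then 4 × 9 + 2 × 9 = 54 g with two maintenance applications in the window, below 60 g.

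**5. Maintenance alone.** 15 g every day is 15 × 4 = 60 g in 4 days, which is not more than one can. The weekly amount is 15 × 7 = 105 g, and 105 / 30 = 3.5 times the maximum. Supply limits this: 3 × 60 = 180 g lasts 180 / 15 = 12 days. Averaged over 4 weeks the supply is 180 / 4 = 45 g/week, or 45 / 30 = 1.5 times the maximum.

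**6. The two sentences of section 9.3.2 against each other.** A single maintenance day above 15 g and up to 60 g, with nothing further in the 4 days, is an overdose under the per-day sentence but not under the can rule. Daily applications of 15 g exceed neither figure; only the weekly maximum and the twice-weekly schedule are breached, and the general sentence has no weekly basis.

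**The case against.** The strongest reply is that the threshold is well founded and the conflict sits at the edge. It equals the 15 g/day label maximum quoted in section 3.3.3 and the 7-can supply, and it agrees with 100 g/week given evenly. In relapse the two products go on different skin. Section 3.3.3 says 15 g covers more than 30% of BSA, and entry is limited to 2-30%, so both maxima at once should be uncommon. The rule can also be read per product, since the two supplies are labelled in different colours. Inclusion criterion 3 speaks of at most 100 g of trial medication a week, which might be taken as a total.

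For maintenance, the per-day sentence already catches any day above 15 g. Extra application days can be entered as medication error (section 9.3.3) or misuse (section 9.3.4) on the same AE form.

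Most of this stands, and it limits the size of the problem. It does not settle the wording. Neither the label figure nor the eligibility criterion is stated as the dosing limit in relapse, and section 9.3.2 does not say whether counting is per product or pooled.

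A reader might infer three stronger things that the documents do not support:

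- **Compliant relapse use will routinely generate overdose AEs, mainly on vehicle.** At the reported average it would not, and more relapses on vehicle is the trial hypothesis, not a known input.
- **Excess maintenance exposure will go unreported.** Other reporting categories exist.
- **Exposure comparisons between arms are compromised.** Returned cans are weighed (protocol section 10.7.1; SAP section 5.5.2), and SAP section 5.5.1 summarises amounts by arm independently of overdose entries.

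**Conclusion.** The point holds as an inconsistency in a stated reporting threshold. The rule suits once-daily treatment. It does not match Table 13 in two situations: combined use in relapse, where use within both limits can reach 72 to 87 g against 60 g, and maintenance alone, where 105 g/week against a 30 g/week maximum does not meet the rule.

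The relapse half assumes that the products are pooled and used near their maxima; rescue product alone conflicts only if used unevenly. The maintenance half assumes extra application days at no more than 15 g each, and full daily use can last only 12 days on one 4-week supply.

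The consequence is limited to how events are labelled. Overdose entries could be inconsistent between relapse and remission periods, and between arms if relapse rates differ. The number affected cannot be derived from the documents and may be small. No efficacy endpoint is touched, no test of AEs is planned (SAP section 5.5.3), and measured exposure does not change.

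**What to change.** Reconcile protocol section 9.3.2 with Table 13 and with sections 3.3.3, 10.2 and 10.4, so that the overdose definition agrees with the maximum stated for each phase. State whether rescue and maintenance product are counted together or separately during relapse, and how the per-day sentence and the 4-day rule relate. Which figures should apply is for the sponsor's clinical and safety functions; this review proposes no dose and no threshold.

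If conduct is too far advanced to amend the protocol, document in the SAP, before unblinding, how overdose, medication error and misuse records will be classified and read in the tables split by rescue use.

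The cost is a wording clarification. No new data are needed.
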